2.3 Imputation Algorithm

It is reasonable to assume the missing values of the longitudinal data for an outcome variable (e.g., PASI, the original scale of PASI 90, at each post-baseline visit) follows a monotone missing pattern. In practice, the missing data of the outcome variable might have an arbitrary (non-monotone) missing data pattern. An extra step may be added accordingly, to augment data into a monotone missing pattern.

For the outcome variable (e.g., PASI at each visit), K 'complete' datasets can be generated in two steps: augmentation step and imputation step. K, the number of repetitions, is determined below.

Augmentation Step

For datasets with non-monotone missing data pattern, the augmentation step will first impute enough values to augment the data into a monotonic missing pattern:

Markov Chain Monte Carlo (MCMC) will be applied to augment the data using PROC MI with the MCMC IMPUTE=monotone statement, assuming a multivariate normal distribution. The augmented data will be used in the subsequent imputation step to generate 'complete' datasets.

- For analyses for the ITT_A Population: Covariates included in the model are treatment group, Baseline body weight as a continuous variable, prior exposure to any systemic and/or biologic treatment for PsO (0, \geq 1), Baseline and all post-baseline visits of the outcome variable up to the end of Period A.
- For analyses for the ITT_B_Combined, ITT_B_NR and ITT_B_R Populations: Covariates included in the model are treatment group, PASI score at Baseline and at the Entry of Period B, and the outcome variable collected at the Entry of Period B and all later visits.

- For analyses for the ITT_LT Population: Covariates included in the model are treatment group, Baseline body weight as a continuous variable, prior exposure to any systemic and/or biologic treatment for PsO ($0, \geq 1$), PASI score at Baseline and at the Entry of Period B, and the outcome variable collected at the Entry of Period B and all later visits. Subjects randomized to RZB at Baseline and did not enter Period B will be included in the analysis and will be counted as non-responders. To accommodate the 1:1 re-randomization, half (round down to integer) of the subjects randomized to APR at Baseline and did not enter Period B will be included in the analysis and will be counted as non-responders.

Of note, categorical variables are included using the form of dummy variables.

Repeat the imputation process $K=30$ times using the procedure described above to form $K=30$ monotone missing datasets, where K is determined as described in "Repetition of Imputations (K)."

Imputation Step

For missing data with monotone missing patterns, the choice of multiple imputation using a parametric regression model that assumes multivariate normality is appropriate.

The imputation step is described below:

- The imputation model for the missing data is a regression model, which controls for the same variables for each Population as listed in the augmentation step. The covariates included in the model and the order of these variables are consistent with the augmentation step.
- For each monotone missing dataset, using SAS PROC MI with MONOTONE REG model statement, the outcome variable at each post-baseline visit with missing values will be imputed sequentially with covariates constructed from their corresponding sets of preceding variables.

A 'complete' dataset with imputed values for the missing data is generated after the augmentation and imputation steps are completed.

Repetition of Imputations (K)

Repetition of imputations, K, must be determined in advance. When estimating the overall variance of multiple imputation, the additional sampling variance is the between-imputation variance divided by K. This value represents the sampling error associated with the overall or average coefficient estimates. It is used as a correction factor for using a specific number of imputations. The more imputations (K) are conducted, the more precise the parameter estimates will be. For example, with a 1% power falloff tolerance in multiple imputation, as compared to an infinite number of imputations, multiple imputation requires 20 repetitions of imputation for 30% missing information and 40 repetitions for 50% missing information (Graham, Olchowski, and Gilreath 2007⁴). In the usual clinical settings expecting less than 30% missing information, K=30 repetitions are deemed sufficient. When missingness exceeds 30%, depending on the power falloff tolerance level, number of repetitions may need to be increased. Recent research⁴ suggested that the number of repetitions (K) should be at least equal to the percentage of missing (White et al., 2011⁶)

2.4 Derivation of Response Status and Non-Responder Imputation

For each 'complete' dataset, the imputed post-baseline values will be rounded to the same precision as the observed data. Response status (e.g., PASI 90 at each visit) will be determined accordingly.

The imputed response status for missing due to reasons other than COVID-19 will be overridden by non-responder imputation (Section 2.1) to ensure that multiple imputation is only applied to missing due to COVID-19:

- Using NRI approach, all missing due to reasons other than COVID-19 will be categorized as non-responders. In addition, subjects whose change/percent

change from Baseline cannot be calculated because of a missing Baseline will be considered as a non-responder at all post-baseline visits, unless the post-baseline value is zero.

- The only exception is that a subject will be categorized as a responder for the visit if the subject is a responder both before and after an SAP-specified visit window in the particular Study Period.

2.5 Analysis

For the ITT_A and ITT_LT Populations: The statistical analysis will use the Cochran-Mantel-Haenszel (CMH) test adjusting for the actual values of stratification factors at Baseline: Baseline body weight (≤ 100 kg, > 100 kg), prior exposure to any systemic and/or biologic treatment for PsO (0, ≥ 1).

For the ITT_B_Combined Population: The statistical analysis will use the CMH test adjusting for the actual values of the stratification factor at re-randomization: PASI 75 response status at the Entry of Period B (Yes/No).

For ITT_B_NR Population: The statistical analysis will use the Chi-square test.

For ITT_B_R Population: Summary statistics will be calculated. No statistical comparison is conducted.

2.5.1 Analysis of Each Dataset

For each of the K 'complete' datasets, the statistical tests as specified above will be used to estimate the treatment difference between treatment groups and the corresponding standard error (except for ITT_B_R Population, in which only summary statistics of each group will be calculated).

2.5.2 Synthesis of Results for Statistical Inference

The results from the K 'complete' datasets will be synthesized using the SAS procedure PROC MIANALYZE, following Rubin's formula (Rubin, 1987⁵), to derive the MI estimator of the treatment difference for the final inferences.

Rubin's formula

We fit the analysis model to the kth 'complete' dataset, denoting the estimate of the treatment difference q by $\tilde{\theta}_k$ from the kth 'complete' dataset, and denoting the corresponding estimate of the variance as V_k .

The MI estimator of q (point estimator obtained from PROC MIANALYZE), $\tilde{\theta}_{MI}$, is the average of the K individual estimators:

$$\tilde{\theta}_{MI} = \frac{1}{K} \sum_{k=1}^K \tilde{\theta}_k.$$

The estimated variance of $\tilde{\theta}_{MI}$, is a combination of the between- and within-imputation variability as follows:

$$V_{MI} = W + \left(1 + \frac{1}{K}\right)B$$

Where $W = \frac{1}{K} \sum_{k=1}^K V_k$ is the within-imputation variability and $B = \frac{1}{K-1} \sum_{k=1}^K (\tilde{\theta}_k - \tilde{\theta}_{MI})^2$ is the between-imputation variance.

It has been shown⁵ that the statistic

$$T = \frac{\tilde{\theta}_{MI} - \theta}{\sqrt{V_{MI}}}$$

has an approximate t_v distribution where $v=(K-1)[(1+W/B)]^2$. Statistical inference, including hypothesis testing and confidence intervals for the treatment effect, will be based on this T-statistic.

3.0 Sample SAS Code

```

/*****/
/*IMPUTATION ALGORITHM*/
/*****/
/*NOTE: THIS APPROACH REQUIRES NO MISSING IN CATEGORICAL COVARIATES AND
REQUIRES AT LEAST ONE OBSERVATION IN BASELINE OR ONE OF THE POST-
BASELINE VISIT*/
/*PASI 90 at Week 16 is used as an example in the sample code*/

/*PRE-AUGMENTATION - CREATE DUMMY FOR CATEGORICAL VARIABLES*/
/*****/
DATA PASI_2; SET PASI;
  /*THE MCMC STATEMENT BELOW ASSUMES MULTI-VARIATE NORMAL*/
  IF TRT01PN=1 THEN TRT1=1; ELSE TRT1=0;
  /*BASELINE WEIGHT AND PRIOR BIO/SYS CATEGORY*/
  IF PSOBLGN = 1 THEN REG1 = 1 ;ELSE REG1 = 0;
RUN;

/*AUGMENTATION STEP -- TO HAVE 30 MONOTONE MISSING DATASETS*/
PROC MI DATA= PASI 2 OUT= PASI MONO NIMPUTE=30 SEED= 12345 /*ACTUAL
RANDOM SEED PRE-DEFINED AS THE NUMERICAL VALUE OF THE DATE OF FIRST
SUBJECT FIRST DOSE*/
  ROUND=. . . 0.1 0.1 0.1 /*VALUE ROUND TO 1ST DECIMAL*/
  MIN=. . . 0 0 0 /*MINIMUM VALUE OF PASI IS 0*/
  MAX=. . . 72 72 72 /*MAXIMUM VALUE OF PASI IS 72*/
MCMC IMPUTE=MONOTONE ;
/*NOTE: CATEGORICAL VARIABLES SUCH AS TRT1 TRT2 ARE DUMMY, CREATED
ABOVE*/
/*NOTE: ALL OTHER NON-DUMMIED COVARIATES MUST BE CONTINUOUS*/
/*SUPPOSE STRATAN (NUMERIC VARIABLE FOR STRATA) HAS ONLY 2 LEVELS, NO
NEED TO CREATE DUMMY*/
VAR TRT1 REG1 WTBL BASE WK4 WK16;
/*CAUTION TO USE THE "BY" STATEMENT IN MCMC: */
/*MVN MODEL IS FITTED WITHIN EACH 'BY' GROUP, INSTEAD OF ACROSS ALL
GROUPS*/
RUN;

/*IMPUTATION STEP - DETERMINE IMPUTATION DISTRIBUTION AND RANDOMLY
IMPUTE MISSING VALUE TO GENERATE 'COMPLETE' DATASETS*/
/*****/
```

```
PROC MI DATA= PASI MONO OUT= PASI FULL NIMPUTE=1 SEED= 54321 /*ACTUAL
RANDOM SEED PRE-DEFINED AS THE NUMERICAL VALUE OF THE DATE OF LAST
SUBJECT FIRST DOSE */
  ROUND= . . . 0.1 0.1 0.1 /*VALUE ROUND TO 1ST DECIMAL*/
  MIN=. . . 0 0 0 /*MINIMUM VALUE OF PASI IS 0*/
  MAX=. . . 72 72 72 /*MAXIMUM VALUE OF PASI IS 72*/
  MINMAXITER=1000;
  /*CLASS CATEGORICAL VARIABLES TRT1 AND REG2*/
  CLASS TRT1 REG1;
  VAR TRT1 REG1 WTBL BASE WK4 WK16;
  MONOTONE REG (WK4 WK16); /* IMPUTED SEQUENTIALLY, FROM WK 4 TO 16,
WITH COVARIATES CONSTRUCTED FROM THE CORRESPONDING PRECEDING VARIABLES*/
  BY IMPUTATION ; /*FOR EACH OF THE 30 MONOTONE
MISSING DATASETS, IMPUTE A 'COMPLETE' DATASET*/
RUN;

/*DETERMINE DICHOTOMOUS RESPONSE STATUS, PASI 90 AT WEEK 16*/
DATA ALL; SET PASI FULL;
  IF 0<=WK16<=0.1*BASE THEN PASI90_16=1;
  ELSE PASI90_16=0;
RUN;

/*****
*/
/*          DATA HANDLING STEPS TO MERGE COVID-19 STATUS OMITTED
*/
/*          PLACE TO ADD DATA HANDLING AND MERGING STEPS
*/
/*****
*/

/*FOR MI, SKIP THE FOLLOWING CODE, PROCEED TO THE CODE AFTER ANALYSIS
MODEL *//*OVERRIDE MISSING VALUES NOT DUE TO COVID-19 WITH TRADITIONAL
NRI*/
DATA ALLF; SET ALL;
  /*COVID19_XX='Y' IF MISSING AT WEEK XX IS DUE TO COVID-19; IF NOT,
OVERRIDE WITH TRADITIONAL NRI*/
  /*VARIABLE PASI90 NRI XX: TRADITIONAL NRI DATA AT WEEK XX, WHICH
COVERS THE SPECIAL HANDLING SUCH AS THE BEFORE-AND-AFTER EXCEPTION IN
THE PARTICULAR STUDY PERIOD*/
  IF COVID19_16 NE 'Y' THEN PASI90_16= PASI90NRI_16;
RUN;
PROC SORT DATA=ALLF; BY _IMPUTATION_ SUBJID; RUN;

/*****
/*ANALYSIS MODEL*/
/*****
```

```
/*KEY CODE: ANALYZING EACH 'COMPLETE' DATASET*/  
/*****  
/*INDIVIDUAL-LEVEL DATA --> # OF RESPONDERS & # OF SUBJECTS, TO BE READ-  
IN TO PROC STD RATE*/  
PROC FREQ DATA=ALL;  
  BY IMPUTATION ;  
  TABLES TRT01PN*STRATAN* PASI90 16/LIST NOCUM NOPRINT OUT=COUNT_TABLE;  
  /*WEEK 16 RESULTS AS AN EXAMPLE*/  
RUN;  
DATA COUNT_TABLE; SET COUNT_TABLE;  
  DROP PERCENT;  
RUN;  
PROC TRANSPOSE DATA=COUNT_TABLE OUT=FREQ_TABLE PREFIX=RESP;  
ID PASI90_16;  
BY IMPUTATION_ TRT01PN STRATAN;  
VAR COUNT;  
RUN;  
DATA FREQ_TABLE1; SET FREQ_TABLE;  
  CASE=RESP1;  
  SIZE=SUM(RESP0, RESP1);  
  KEEP _IMPUTATION_ TRT01PN STRATAN CASE SIZE;  
RUN;  
  
/*RE-ORDER TO SET 1 (PLACEBO) AS THE REFERENCE GROUP*/  
DATA FREQ_TABLE2; SET FREQ_TABLE1;  
  IF TRT01PN=2 THEN TRT01PN=0;  
RUN;  
  
/*CALCULATE THE COMMON RISK DIFF FOR EACH COMPLETE DATASET*/  
PROC STD RATE DATA=FREQ_TABLE2  
  METHOD=MH STAT=RISK EFFECT=DIFF;  
  BY _IMPUTATION_;  
  POPULATION GROUP=TRT01PN EVENT=CASE TOTAL=SIZE;  
  STRATA STRATAN / ORDER=DATA STATS(CL=NONE) EFFECT;  
  ODS OUTPUT EFFECT=EFFECT;  
RUN;  
  
/*COMBINING RESULTS USING PROC MIANALYZE*/  
/*****  
PROC MIANALYZE DATA=EFFECT;  
  ODS OUTPUT PARAMETERESTIMATES=RISK_DIFF_MH;  
  MODELEFFECTS RiskDiff;  
  STDERR StdErr;  
RUN;
```

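### The SAP Appendix D sample code for PASI 90 at Week 16 writes the non-responder override to ALLF but analyses ALL, so as printed it runs plain multiple imputation and not the specified NRI-MI

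*SAP*

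**What the plan says.** Protocol 7.4 names NRI-MI as the missing-data method for the primary and ranked secondary endpoints. SAP 9.2.1 and Appendix D 2.1 define it. A subject without an evaluation in the visit window is a non-responder, with two exceptions: a subject who responds both before and after the window within the same study period, and a value missing because of COVID-19, which is multiply imputed. Appendix D 2.4 requires the imputed status for all other missing values to be overridden, "to ensure that multiple imputation is only applied to missing due to COVID-19".

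Appendix D 3.0 then prints sample SAS code, with the scope note "PASI 90 at Week 16 is used as an example in the sample code". The relevant steps, in order, are:

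- "DATA ALL; SET PASI FULL" derives the response from the completed PASI values, whatever the reason for missingness.
- A comment, "FOR MI, SKIP THE FOLLOWING CODE", introduces the override block.
- "DATA ALLF; SET ALL" opens a new dataset, in which "IF COVID19_16 NE 'Y' THEN PASI90_16= PASI90NRI_16" applies the override.
- "PROC SORT DATA=ALLF; BY _IMPUTATION_ SUBJID; RUN" sorts that dataset. This is its last printed use.
- "PROC FREQ DATA=ALL" opens the analysis model.

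**The concern.** The override that turns multiple imputation into NRI-MI sits in a dataset that the analysis never reads. The printed code therefore contradicts the method it is meant to illustrate, and it is the only code given for NRI-MI. The example is a Period A co-primary endpoint. A programmer who adapts it line by line would report a treatment difference and confidence interval based on a missing-at-random assumption for every missing value, including withdrawals unrelated to COVID-19, for which the plan prescribes non-response.

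**Working it through.** **1. Trace of the datasets.** Reading backwards from the final estimate, each dataset is built from the one to its right:

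`RISK_DIFF_MH` ← `EFFECT` ← `FREQ_TABLE2` ← `FREQ_TABLE1` ← `FREQ_TABLE` ← `COUNT_TABLE` ← `ALL` ← `PASI_FULL` ← `PASI_MONO` ← `PASI_2` ← `PASI`

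`ALLF` is not in this chain, so the override does not reach PROC STDRATE or PROC MIANALYZE. If PROC FREQ read `ALLF`, the chain would run `COUNT_TABLE` ← `ALLF` ← `ALL` and Appendix D 2.4 would be met.

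**2. Which dataset was meant.** The comment says the override block is skipped for plain MI, so `ALL` is the plain-MI input and `ALLF` the NRI-MI input. `ALLF` is also sorted by imputation number immediately before a PROC FREQ that runs by imputation number, and nothing else printed uses that sort.

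**3. Size.** The documents give 110 vs 220 subjects and a difference of at least 40 points for Period A (SAP 2.4). They give no arm-level Week 16 rates and no missingness rates, so the following are assumptions:

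- *q*: response among observed subjects, 60% on risankizumab (R) and 20% on apremilast (A)
- *m*: share of the arm missing at Week 16
- *c*: share of the missing values that is due to COVID-19
- *r*: imputed response rate of missing subjects as a fraction of *q*

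Week 16 is the last visit of Period A, so the before-and-after exception is taken not to apply. Expected rate per arm:

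- from `ALL`: q(1 − m) + r·q·m
- from `ALLF`: q(1 − m) + r·q·m·c
- overstatement of the difference by the code: r(1 − c)(q_R·m_R − q_A·m_A)

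| m_R / m_A | c | r | `ALL` difference | `ALLF` difference | Code minus NRI-MI |
|---|---|---|---|---|---|
| 5% / 5% | 0 | 1 | 40.0 | 57.0 − 19.0 = 38.0 | +2.0 |
| 10% / 10% | 0 | 1 | 40.0 | 54.0 − 18.0 = 36.0 | +4.0 |
| 5% / 5% | 0.2 | 1 | 40.0 | 57.6 − 19.2 = 38.4 | +1.6 |
| 10% / 10% | 0.2 | 1 | 40.0 | 55.2 − 18.4 = 36.8 | +3.2 |
| 10% / 10% | 0 | 0.5 | 57.0 − 19.0 = 38.0 | 54.0 − 18.0 = 36.0 | +2.0 |
| 5% / 15% | 0 | 1 | 40.0 | 57.0 − 17.0 = 40.0 | 0.0 |
| 5% / 25% | 0 | 1 | 40.0 | 57.0 − 15.0 = 42.0 | −2.0 |

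The gap is zero if nothing is missing or if all missingness is due to COVID-19 (c = 1). At 60% vs 20% it changes sign once apremilast missingness exceeds three times that on risankizumab.

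**4. Scale.** The 95% half-width from `ALL`, before between-imputation variance, is 1.96 × √(0.6 × 0.4/110 + 0.2 × 0.8/220) = 10.6 points. Even at 51% vs 19%, below every `ALLF` difference in the table, the chi-square test with 110 vs 220 has about 99.996% power.

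**The case against.** The strongest reply is that this is labelled sample code and is visibly a template. It says that data-handling steps are left out, it mentions variables it never creates, and it labels a reference group as placebo in a trial without placebo. The method is stated correctly in protocol 7.4, SAP 9.2.1 and Appendix D 2.1 and 2.4, and the code's own comment ties the override to NRI. Harm needs a programmer to follow one dataset name against all of that. This stands as a limit on the weight of the point. It does not remove the contradiction: the omitted steps come before `ALLF` is created, so they cannot change which dataset the analysis reads.

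A letter lost in text extraction is also possible, since the extraction drops underscores in this code. It is unlikely, because `ALLF` is intact in both of its other uses, but the source PDF should be checked.

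Plain MI might have been intended as a sensitivity analysis. SAP 9.2 and Appendix D 1.1 mention such analyses in general, but SAP 9.3.3 plans none for the primary endpoints, and the main analysis needs `ALLF` in any case.

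A reader might infer three stronger things that the documents do not support:

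- *That the Period A analysis is or will be wrong, or that efficacy will be overstated.* No production program is shown, and the direction of the shift depends on the missing-data pattern.
- *That shifts as large as 8 points are to be expected.* That needs, for example, 15% missing on risankizumab and 5% on apremilast (40 against 51.0 − 19.0 = 32), which no document suggests. The model also conditions on Week 4 PASI, so subjects doing poorly before dropout would be imputed lower than the observed rate.
- *That the code has two further errors.* The override looks only at the COVID-19 flag, so a subject with prior alternative psoriasis treatment might keep an imputed response, against SAP 8.0. That depends on how the flag is set in steps the code says are omitted. The responder count is also left missing, not zero, in a treatment-by-stratum cell with no responders, but no effect on the estimate has been shown. Such a cell is rare unless strata are small: at an assumed 20% response, 0.80^15 = 3.5% with 15 apremilast subjects, and 0.80^55 = 0.0005% with an even split of 220 over four strata. Both are coding checks.

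**Conclusion.** The point holds as a contradiction between code and text. As printed, the sample code for a co-primary endpoint runs multiple imputation for all missing data, whereas the plan specifies NRI-MI. The prose governs, and nothing indicates that the production program repeats the slip.

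If the code were followed, the Period A estimate and confidence interval would belong to a different method. The illustrative overstatement is about 2 to 4 points at 5% to 10% equal missingness. It rests on assumed rates of 60% vs 20%, no COVID-19 missingness and imputation at the observed rate, and is at the upper end for equal missingness at those levels. It shrinks as the COVID-19 share rises or if dropouts are imputed lower, and it can reverse with much higher apremilast missingness. At the planned effect the test conclusion is not expected to change.

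**What to change.** In Appendix D 3.0, change the first step of the analysis model to `PROC FREQ DATA=ALLF` and state in a comment that `ALL` is the input for a plain-MI run only. Check the dataset name against the source PDF, and confirm that the production programs read the overridden dataset.

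As coding checks, confirm that the omitted COVID-19 merge step keeps subjects with a prior SAP 8.0 intercurrent event as non-responders whatever the COVID-19 flag, and set `CASE=SUM(RESP1,0)` so that a cell with no responders counts as 0.

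The cost is a few lines of sample code and one check of the production programs. The prose method and trial conduct do not change.

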2.4 Sample Size Determination

This study plans to enroll a total of $N = 330$ subjects, to be sufficiently powered to detect the treatment difference between risankizumab (RZB) and apremilast (APR) with respect to the co-primary endpoints in Period A, as well as between APR/RZB and APR/APR with respect to the primary endpoint in Period B:

- Assuming that 50% of APR-PASI75NR subjects in the APR/RZB group and 20% of APR-PASI75NR subjects in the APR/APR group will achieve PASI 90 at Week 52 in Period B, the sample size of 120 re-randomized APR-PASI75NR subjects (60 subjects per group) will have more than 90% power to detect the treatment difference between APR/RZB and APR/APR, using a Chi-square test with a 2-sided significance level of 0.05.
- Assuming 55% of subjects initially randomized to APR will be re-randomized at Week 16 under the APR-PASI75NR (as defined by the PASI 75 response at Week 16) stratum, the total sample size for the initial APR group is $120/55\% = 220$. Assuming the treatment difference is at least 40% with respect to the co-primary endpoints of PASI 90 and sPGA of 0 or 1 at Week 16 in Period A, the total sample size of $N = 330$ subjects (RZB: 110, APR: 220) will

also provide more than 90% power to detect the treatment difference between RZB and APR, using a Chi-square test with a 2-sided significance level of 0.05.

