4.0 Analysis Populations

The following analysis populations will be used for the analyses.

The Intent to Treat Population in Period A (ITT_A) includes all randomized subjects. The ITT_A Population will be used for all efficacy analyses in Period A.

The Intent to Treat Population for APR-PASI75NRs in Period B (ITT_B_NR) includes subjects randomized at Baseline (Day 1), fail to achieve PASI 75 at Week 16 and are re-randomized. The ITT_B_NR Population will be used for the analysis comparing switch-to-RZB (APR/RZB) vs. continue-with-APR (APR/APR) among APR-PASI75NRs in Period B.

The Intent to Treat Population for APR-PASI75 responders in Period B (ITT_B_R) includes subjects randomized to APR at baseline, achieve PASI 75 at Week 16 and are re-randomized (APR-PASI75Rs). The ITT_B_R Population will be used for the summary of efficacy for APR/RZB and APR/APR among APR-PASI75Rs in Period B.

The Intent to Treat Population for Period B combined Population (ITT_B_Combined) includes subjects randomized to APR at Baseline and are re-randomized at Week 16. The ITT_B_Combined Population will be used for combined analysis (APR-PASI75NRs and APR-PASI75Rs) between subjects re-randomized to APR/RZB and APR/APR in Period B.

The Intent to Treat Population for Long Term Efficacy (ITT_LT) includes subjects randomized to receive continuous RZB (i.e., all subjects randomized to RZB at Baseline) and subjects randomized and re-randomized to receive continuous APR, including half of the subjects randomized to APR at Baseline and prematurely discontinued from study before entering Period B. The ITT_LT Population will be used for the analysis comparing long term efficacy between continuous treatment of RZB/RZB and APR/APR in Period B. Of note, the algorithm to select half of the subjects randomized to APR at Baseline and prematurely discontinued from study before entering Period B is defined as follow:

1. Rank all such subjects by their subject ID in ascending order (as 1, 2, 3...).
2. Select subjects whose ranks are even numbers.

The Intent to Treat Population for Rescued Population (ITT_Res) includes subjects who are re-randomized to APR at Week 16, fail to achieve PASI 50 at Week 28 and/or Week 40, and receive RZB as the rescue medication. The ITT_Res Population will be used for the summary of efficacy after being rescued with RZB.

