9.0 Efficacy Analyses

9.1 General Considerations

All efficacy analyses will be conducted among the ITT Population in each analysis period. All tests will be 2-sided at an alpha level of 0.05.

The Primary Analysis for Period A will be performed after all ongoing subjects have completed Week 16 and all data pertaining to Period A are cleaned. This will be the only and final analysis for efficacy in Period A.

The Primary Analysis for Period B will be performed after all ongoing subjects have completed Week 52 and all data pertaining to Period B are cleaned. This will be the only and final analysis for efficacy in Period B.

The final analysis will be performed upon study completion.

Categorical Endpoints:

For categorical endpoints, the number and proportion of subjects who achieved the endpoint, as well as the 95% confidence interval (CI) of that proportion, will be provided by each treatment group among all ITT Populations.

In addition, comparisons between treatment groups will be made in the following analyses, with the estimated treatment difference, as well as the corresponding 95% CI and the p-value provided among the following populations:

- ITT_A Population: Comparisons in Period A will be made between RZB and APR using the Cochran-Mantel-Haenszel (CMH) test, adjusting for the actual values of stratification factors at Baseline: Baseline body weight (≤ 100 kg, > 100 kg) and prior exposure to any systemic and/or biologic treatment for psoriasis ($0, \geq 1$). In case of any stratum with zero subject in either treatment group, no stratification factor will be controlled.
- ITT_B_NR Population: Comparisons in Period B will be made between APR/RZB and APR/APR using the chi-square test.

- ITT_B_Combined Population: Comparisons in Period B will be made between APR/RZB and APR/APR using the CMH test, adjusting for the actual values of the stratification factor of re-randomization: PASI 75 response status at Week 16 (Yes/No). In case of any stratum with zero subject in either treatment group, no stratification factor will be controlled.

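### The SAP's sample code passes a stratum with no responders to the Mantel-Haenszel step as a missing event count instead of 0 of n

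*SAP*

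**What the plan says.** SAP 4.0 defines ITT_A as all randomised subjects and adds: "The ITT_A Population will be used for all efficacy analyses in Period A". SAP 9.1 and Appendix D 2.5 specify a CMH comparison adjusted for baseline weight (two levels) and prior systemic or biologic exposure (two levels), which gives four strata. SAP 9.1 has one rule for sparse strata: "In case of any stratum with zero subject in either treatment group, no stratification factor will be controlled". That rule concerns strata without subjects, not strata without responders.

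Appendix D 3.0 shows how the adjusted difference and its standard error are obtained in each imputed dataset. The steps are:

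- PROC FREQ counts subjects by arm, stratum and response into an output dataset, without the SPARSE option.
- PROC TRANSPOSE spreads the counts into `RESP0` and `RESP1`.
- A data step sets `CASE=RESP1` and forms the denominator with "SIZE=SUM(RESP0, RESP1".
- PROC STDRATE takes `CASE` as the event count and `SIZE` as the total, and the results go to PROC MIANALYZE.

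No later line resets a missing `RESP1`.

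**The concern.** A cell with n subjects and no responders is valid data and should enter the analysis as 0 of n. As printed, it enters as a missing event count with a total of n. The cell most exposed is a small apremilast stratum on PASI 90 at Week 16.

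If the record is not used, that stratum has only one arm left and cannot contribute a difference. Randomised subjects from both arms would then leave a co-primary estimate because of the outcome observed. The reported difference, its confidence interval and the number analysed would no longer be those of the CMH analysis in SAP 9.1. The CMH analyses of ITT_LT and ITT_B_Combined carry the same exposure if they are programmed from this template.

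**Working it through.** **1. The plan's own figure.** SAP 2.4 gives arm sizes "RZB: 110, APR: 220" and an effect described as "Assuming the treatment difference is at least 40% with respect to the co-primary endpoints". It says these "also provide more than 90% power to detect the treatment difference between RZB and APR". SAP 9.1 sets the level: "All tests will be 2-sided at an alpha level of 0.05". The arm rates are not given, so take 50% against 10% as one case, with a pooled-variance chi-square test:

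- Pooled rate = (55 + 22)/330 = 0.2333.
- SE under the null = √[0.2333 × 0.7667 × (1/110 + 1/220)] = 0.0494.
- SE under the alternative = √(0.25/110 + 0.09/220) = 0.0518.
- z = (0.40 − 1.96 × 0.0494)/0.0518 = 5.85, so power is above 99.9%.

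Power stays above 99.9% for apremilast rates from 2% to 50% with a 40-point difference. The stated power is reproduced and is not in dispute.

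**2. What the code does to a zero cell.** The counting and transposing logic was followed outside SAS.

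| Cell | RESP0 | RESP1 | CASE | SIZE |
|---|---|---|---|---|
| 0 responders of 22 | 22 | missing | missing | 22 |
| 11 responders of 11 | missing | 11 | 11 | 11 |

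Only the zero-responder case goes wrong, because the sum protects `SIZE` and nothing protects `CASE`.

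**3. How likely a zero cell is.** With rate p in every stratum, the chance that an apremilast stratum of size n has no responder is (1 − p)^n. The chance of at least one such stratum is 1 − Π[1 − (1 − p)^n]. The rates and the splits of 220 below are assumptions.

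| Assumed apremilast strata | p = 2% | 5% | 10% | 20% |
|---|---|---|---|---|
| 99/66/33/22 | 89% | 47% | 13% | 0.8% |
| 110/66/31/13 | 93% | 63% | 28% | 5.6% |
| 55/55/55/55 | 80% | 22% | 1.2% | about 0% |

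Check of one entry (first row, 5%): the four zero-cell chances are 0.006, 0.034, 0.184 and 0.324, and 1 − 0.994 × 0.966 × 0.816 × 0.676 = 0.47.

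**4. What would change if the record is excluded.** Assumed counts: risankizumab 25/50, 16/33, 7/16, 3/11; apremilast 8/99, 5/66, 2/33, 0/22. The Mantel-Haenszel weight is w = n₁n₀/(n₁ + n₀), and the difference is Σw(p₁ − p₀)/Σw.

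| Stratum | w | p₁ − p₀ | w × difference |
|---|---|---|---|
| 1 | 33.22 | 0.4192 | 13.93 |
| 2 | 22.00 | 0.4091 | 9.00 |
| 3 | 10.78 | 0.3769 | 4.06 |
| 4 | 7.33 | 0.2727 | 2.00 |

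- Stratum 4 excluded: 26.99/66.00 = 40.9% (95% CI 30.4 to 51.4), on 297 subjects.
- Stratum 4 kept as 0 of 22: 28.99/73.33 = 39.5% (29.7 to 49.3), on 330 subjects.

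The exclusion raises the estimate by 1.4 points. If risankizumab in stratum 4 is 8/11 instead, the excluded result is still 40.9%, but the full result is (26.99 + 5.33)/73.33 = 44.1% (34.3 to 53.9). The exclusion then lowers the estimate by 3.2 points. The intervals use simple binomial variances within strata.

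**The case against.** The strongest objection is that the harmful step is not in the documents. They do not say how PROC STDRATE treats a missing event count, and SAS was not run. A reader might infer that the stratum is certain to be lost. The text does not support that. It supports only that the input is wrong, and every figure for excluded subjects or a shifted estimate is conditional on exclusion.

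Second, the governing text is right. A stratum with 0 of n is an ordinary CMH stratum, so SAP 9.1 needs no extra rule. This stands: the fault is in the code, not in the specified method.

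Third, the block is headed as sample code, uses PASI 90 as an example and still carries leftovers from a template. That lowers its weight but does not remove the point. It is marked as the key code for analysing each completed dataset, and it is the only detailed description of how the difference and standard error are produced. The steps it declares omitted come before the counting, so they would not repair it.

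Fourth, the frequencies depend on a low rate. The only apremilast PASI 90 rate in the documents is 20%, at Week 52 among PASI 75 non-responders. That is another time and subset, but at 20% a zero cell is rare in all three splits. This stands, and is why the range is shown.

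A reader might also infer spurious variance between imputations, with a stratum present in some of the 30 datasets and absent in others. Under Appendix D 2.4, imputed values are kept only for COVID-19-related gaps. This would therefore need a stratum whose observed apremilast subjects are all non-responders and which also contains such a gap. Nothing in the documents gives that a probability.

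Finally, the comment "RE-ORDER TO SET 1 (PLACEBO) AS THE REFERENCE GROUP" names a placebo that this trial does not have. It is not executed, and SAP 2.1 already fixes the contrast as risankizumab compared with apremilast. It is clerical.

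**Conclusion.** The point holds as a coding defect. As printed, an arm-by-stratum cell with no responders gives a missing event count with a total of n, where the specified analysis of all ITT_A subjects requires 0 of n. Loss of the stratum follows only if the procedure excludes that record.

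On that condition, the estimate could move by a few points in either direction (+1.4 and −3.2 in the two examples), with 33 of 330 subjects lost in each. How often it would arise depends on undocumented rates and stratum sizes: likely at apremilast rates of a few per cent, rare at 20%. The calculation depends only on the rate, so it applies to any of the stratified binary endpoints. No rate for sPGA 0 or 1 at Week 16 is documented either.

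It would be wrong to conclude that the co-primary test is at risk. With power above 99.9% for a 40-point difference, the significance conclusion is unlikely to change. What is exposed is the reported difference, its interval and the number analysed. The Period B primary and ranked secondary comparisons use an unstratified chi-square test and cannot lose a stratum this way.

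**What to change.** In SAP Appendix D 3.0, replace `CASE=RESP1` with `CASE=COALESCE(RESP1,0)` or `CASE=SUM(RESP1,0)`. Adding SPARSE to the TABLES statement is an alternative. Carry the same change into the production programs for ITT_A, ITT_LT and ITT_B_Combined, and run one test dataset with a zero-responder cell to confirm that all randomised subjects are counted. No new rule in SAP 9.1 is needed. The placebo comment can be corrected to apremilast at the same time. The cost is one line of code and one test run before database lock, with no effect on trial conduct.
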